6.6 Surveillance for SARS-CoV-2 Infection

In concert with the collection of AEs, at each visit and the follow-up telephone calls participant will be interviewed for potential symptoms of COVID-19 disease, recent diagnosis of SARS-CoV-2 infection, and for potential exposure to COVID-19. A guide will be used for this process (see Investigator Site File).

Potential symptoms of COVID-19 disease include (at a minimum): fever or chills, cough, shortness of breath or difficulty breathing, fatigue, muscle or body aches, headache, new loss of taste or smell, sore throat, congestion or runny nose, nausea or vomiting, and diarrhea.

Participants should be reminded to contact the site within 24 hours if experiencing COVID 19 like symptoms or if exposed to a confirmed COVID-19 case.

7 STATISTICAL CONSIDERATIONS

This section summarizes the planned statistical analysis strategy and procedures for the study. The details of statistical analysis will be provided in the SAP, which will be finalized before the first interim analysis. If, after the study has begun, but prior to any unblinding, changes are made to primary and/or key secondary objectives/hypotheses, or the statistical methods related to those hypotheses, then the protocol will be amended (consistent with International Council for Harmonisation [ICH] Guideline E9). Changes to other secondary or exploratory analyses made after the protocol has been finalized, along with an explanation as to when and why they occurred, will be listed in the SAP or CSR for the study. Ad hoc exploratory analyses, if any, will be clearly identified in the CSR.

Data collected after ARCT-021 vaccinations for those participants who originally are randomized to the placebo group (Study Group 4) and who are re-enrolled to receive ARCT-021 will be summarized and presented by dose group in statistical table/listing separately from those participants who complete the study as originally randomized.

7.1 Estimands and Intercurrent Events

Possible intercurrent events are presented in [Table 7-1](#).

Table 7-1 Intercurrent Event Types

Label	Intercurrent Event (IcEv) Type
IcEv1 (Death)	Death due to any cause (including pneumonia) other than COVID-19.
IcEv2 (Missed dose)	Does not receive the second or booster vaccinations at Day 28 and Day 208, respectively.
IcEv3 (Immune-modifying)	Use of immune-modifying drugs or non-study vaccines which interfere with immunogenicity.
IcEv4 (Early infection)	Antigens or antibodies indicating exposure to SARS-CoV-2 prior to vaccination or early infection before Day 7. (This IcEv is particularly relevant to assessing immunogenicity.)
IcEv5 (Study infection)	Develops COVID-19 or asymptomatic SARS-CoV-2 infection on or after Day 7. (This IcEv is particularly relevant to immunogenicity and CESI events.)

Attributes for the primary safety and immunogenicity estimands with strategies for intercurrent events (IcEvs) are presented in [Table 7-2](#).

Table 7-2 Primary Safety and Immunogenicity Estimands With Rationale and Strategies to Address Intercurrent Events

Estimand Label	Estimand 1 (Safety)
Estimand Description	Count and percentage of vaccinated healthy adults who would develop MAAEs, NOCDs, SAEs, AEs leading to discontinuation/withdrawal, solicited AEs, and unsolicited AEs: These will be evaluated after each dose of study vaccine by priming vaccine study group (Group 1, 2, 3, and 4) and by booster vaccine received (ARCT-021, ARCT-154, ARCT-165, or placebo). A treatment policy strategy is used for assessing safety irrespective of an early infection within 7 days after the first vaccination or an infection during the study or missed subsequent vaccination. Infections and death are included in the endpoint (composite strategy).
Target Population	Participants receiving at least 1 dose of study vaccine (as defined by eligibility criteria).
Endpoint	Occurrence of MAAEs, NOCDs, AEs leading to discontinuation/withdrawal, SAEs, solicited, or unsolicited AEs: 
 Solicited AEs within 7 days of each vaccination (by Toxicity Grade, Appendix 13.4): Day 7, Day 35, Day 215 Unsolicited AEs within 28 days of each vaccination (by mild/moderate/severe severity): Day 28, Day 56, Day 236 MAAEs, NOCDs, SAEs, AEs leading to discontinuation/withdrawal from Vaccination 1 to Prior to Vaccination 2, Vaccination 2 to Prior to Booster Vaccination, Overall Prior to Booster Vaccination, and Post-booster Vaccination
Treatment Conditions	Placebo or 5.0 µg or 7.5 µg ARCT-021 administered on Day 0, Day 28; placebo, ARCT-021, ARCT-154, or ARCT-165 administered on Day 208.
Population-Level Summary	Percentage of vaccinated participants (who would develop each type of AE).
Intercurrent Event Strategy	
IcEv1 (Death)	Composite strategy
IcEv2 (Missed dose)	Treatment policy strategy
IcEv3 (Immune-modifying)	Treatment policy strategy
IcEv4 (Early infection)	Treatment policy strategy
IcEv4 (Study infection)	Composite strategy
Rationale for Strategies	Deaths and symptomatic infections during study would contribute as part of the endpoint (ie, included as MAAEs, SAEs, NOCDs, AEs leading to discontinuation/withdrawal, solicited AEs or unsolicited AEs) as per normal practice. A treatment policy strategy is used for assessing safety irrespective of early infection and missed additional (second, booster) study vaccinations.

Arcturus Therapeutics, Inc.
Protocol ARCT-021-04, Version 6.0

ARCT-021
09 March 2022

Estimand Label	Estimand 2 (Geometric Mean Titers/Concentrations)
Estimand Description	
The GMT of NAbs (primary) and GMC of BAbs (secondary) against SARS-CoV-2 up to Early Termination after first vaccination with ARCT-021 of each group (5.0, 7.5 µg, or placebo) and with/without booster dose in healthy adults.
 
Interest will lie in comparing the GMT/GMC of each dosing regimen to placebo based on the Geometric Mean Ratio (GMR).
 
The hypothetical strategy is used to estimate antibody levels had all scheduled vaccinations been received, and without subsequent SARS-CoV-2 infection or influence from immune-modifying drugs or non-study vaccines. The principal stratum strategy excludes those with active or early SARS-CoV-2 infection within 7 days after the first study vaccine administration.

Analysis Population	Vaccinated healthy adults (as defined by eligibility criteria) without active or early SARS-CoV-2 infection (infection within 7 days after the first vaccination).
Endpoint	Total NAbs (primary) and BAbs (secondary) specific for the SARS-CoV-2 measured pre- and post-priming vaccine administration (on Day 0, 14, 28, 42, 56, and 208) and following booster vaccine administration (Day 236, Early Termination).
Treatment Conditions	Placebo or 5.0 µg or 7.5 µg ARCT-021 administered on Day 0, Day 28; placebo, ARCT-021, ARCT-154, or ARCT-165 administered on Day 208.
Population-Level Summary	The GMT, GMC and GMR of comparisons of interest at each time point. GMR will compare responses in placebo-, ARCT-021-, ARCT-154-, and ARCT-165-vaccinated groups at relevant timepoints. For additional considerations on population-level summary see the SAP.
Intercurrent Event Strategy	
IcEv1 (Death)	Hypothetical strategy
IcEv2 (Missed dose)	Hypothetical strategy
IcEv3 (Immune-modifying)	Hypothetical strategy
IcEv4 (Early infection)	Principal stratum strategy
IcEv5 (Study infection)	Hypothetical strategy
Rationale for Strategies	Hypothetical strategy is used to understand antibody levels achieved through receiving scheduled vaccination, without subsequent SARS-CoV-2 infection and without any influence from immune-modifying drugs or non-study vaccines. In estimation, the hypothetical uses a statistical model on the mITT (excluding data points following intercurrent events and not complete removal of all data for the participant).

Estimand Label	Estimand 3 (Rise/Seroconversion)
Estimand Description	Percentage of participants with at least 2- and 4-fold increase in antibody responses from baseline (seroconversion) in NAbs (primary) and BAbs (secondary) at each time point from Day 14 to Early Termination. The hypothetical strategy is used to estimate antibody levels had all scheduled vaccinations been received, and without subsequent SARS-CoV-2 infection or influence from immune-modifying drugs or non-study vaccines. The principal stratum strategy excludes those with active or prior SARS-CoV-2 infection at first vaccination.
Target Population	Vaccinated healthy adults (as defined by eligibility criteria) without active or early SARS-CoV-2 infection within 7 days after first vaccination.
Endpoint	GMFR and seroconversion against SARSCoV-2 NAbs (primary) and BAbs (secondary) measured pre- and post-priming vaccine administration (on Day 0, 14, 28, 42, 56, and 208) and following booster vaccine administration (Day 236, Early Termination).
Treatment Conditions	Placebo or 5.0 µg or 7.5 µg ARCT-021 administered on Day 0, Day 28; placebo, ARCT-021, ARCT-154, or ARCT-165 administered on Day 208.
Population-Level Summary	The GMFR and \geq 2- and 4-fold seroconversion (SC) at each time point.
Intercurrent Event Strategy	
IcEv1 (Death)	Hypothetical strategy
IcEv2 (Missed dose)	Hypothetical strategy
IcEv3 (Immune-modifying)	Hypothetical strategy
IcEv4 (Early infection)	Principal stratum strategy
IcEv5 (Study infection)	Hypothetical strategy
Rationale for Strategies	Hypothetical strategy is used to understand seroconversion achieved through receiving scheduled vaccination, without subsequent SARS-CoV-2 infection and without any influence from immune-modifying drugs or non-study vaccines. In estimation, the hypothetical uses a statistical model on the mITT (excluding data points following intercurrent events and not complete removal of all data for the participant).

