2 STUDY OBJECTIVES AND ENDPOINTS

2.1 Primary Objectives and Endpoints

The primary objective(s) and endpoints are presented in [Table 2-1](#). For estimands, see [Section 7.1](#).

Table 2-1 Primary Objectives and Endpoints

Primary Objectives	Endpoint Description

 To assess the safety and reactogenicity of ARCT-021 compared to placebo for priming vaccination 	
Safety will be evaluated in all participants receiving at least 1 administration of study vaccine (ARCT-021 or placebo) and will be summarized for each vaccination as number and percentage of participants with:
 
 Any unsolicited adverse event (AE) initiating within 28 days after each study vaccine administration, by severity and relationship to study vaccine Any medically attended adverse event (MAAE), new onset of chronic disease (NOCD), AE leading to discontinuation/withdrawal or serious adverse event (SAE) through Early Termination Safety laboratory assessment before and 7 days after each study vaccine administration, by toxicity grade 
Reactogenicity will be evaluated in all participants receiving at least a single administration of study vaccine and will be summarized for each vaccination as number and percentage of participants with:
 
 Any solicited local or systemic AE initiating within 7 days after each study vaccine administration, by toxicity grade

 To assess the neutralizing antibody responses of ARCT-021 compared to placebo for priming vaccination 	
Neutralizing antibody (NAb) responses will be evaluated in all participants receiving at least 1 administration of study vaccine (ARCT-021 or placebo).
 
 Geometric Mean Titer (GMT) measured at all time points Geometric Mean Fold-rise from baseline (GMFR); measured at all time points after baseline (= Day 0) Percentages of participants with ≥ 2- and 4-fold increase in titer from baseline (Seroconversion [SC]); measured at all time points after baseline GMT ratio (ARCT-021/placebo) measured at all time points

 To select the dose and schedule for use in the Phase 3 study in adult participants 	
Safety and reactogenicity data after each priming vaccine administration and immunogenicity responses measured 28 days after each priming vaccination will

Table 2-1 Primary Objectives and Endpoints

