6.4.1.1.7 Clinical Events of Special Interest

Clinical Events of Special Interest (CESI) are events relating to the detection of disease (SARS-CoV-2) activity relevant to the study vaccine. These events are analyzed separately from safety data; however, if the CESI demonstrates untoward signs or symptoms that, in the opinion of the Investigator, suggest the events are more likely related to study vaccine rather than to SARS-CoV-2, these signs/symptoms will be reported as AEs.

To be considered as a CESI of COVID-19 the following case definition adapted from the CBER Guidance: Development and Licensure of Vaccines to Prevent COVID-19 ([DHHS 2020](#)) must be met:

- The participant must have experienced at least 1 of the following systemic symptoms: fever ($\geq 38^{\circ}\text{C}$), chills, myalgia, headache, sore throat, congestion or runny nose, nausea or vomiting, diarrhea, fatigue, new olfactory and taste disorder(s), cough, shortness of breath, or difficulty breathing OR
- Clinical or radiographical evidence of pneumonia; AND
- The participant must have at least 1 test positive for SARS-CoV-2 by RT-PCR.

To be considered as a CESI of asymptomatic SARS-CoV-2 infection, a participant who demonstrates none of the COVID-19 symptoms described above but who tests positive for SARS-CoV-2 on PCR test or anti-nucleocapsid antibody test (if nucleocapsid antibody negative prior to entry into the study) will be counted.

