6.4.1.3.3 Exceptions

Because CESI events are typically associated with the disease under study, they will not be reported as SUSARs even though the event may meet the definition of a SAE. These events will be recorded on the CESI eCRF page in the participant's eCRF.

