7.6.2 Overview of Statistical Methods: Estimation of Estimands and Sensitivity Analyses

A summary of the statistical methods and sensitivity analyses is presented in [Table 7-4](#). Placebo participants will be pooled across dose groups summaries.

Table 7-4 Summary of Statistical Methods and Supportive Analyses

Estimand Label	Estimand Description	Main Estimation			Supportive Analysis
		Analysis Set	Imputation/ Data/ Censoring Rules	Analysis Model/Method	
Estimand 1 (Primary)	
Percentage of vaccinated healthy adults who:
 
 report solicited AEs within the specified timeframe develop unsolicited AEs including MAAEs, etc, within the specified timeframe. 
A treatment policy strategy is used for assessing safety irrespective of a current (or prior) infection at time of first vaccination or missed second vaccination. See Table 7-2 for full definition.
	RAS (solicited AEs) SAS (unsolicited AEs)	Infections and death (if they meet the AE and time window criteria) are included in the endpoint (composite strategy).	Summaries of number of participants (%) with solicited AEs (by toxicity grade), safety laboratory assessments (by toxicity grade), unsolicited AEs (by severity and relatedness to study vaccine), MAAEs, NOCDs, SAEs, and AEs leading to discontinuation/withdrawal will be presented. The Clopper-Pearson 95% CIs will be presented for the incidence rate of these events. See Section 7.6.3.1 and the SAP for further details.	
Supportive: Analysis will be performed for a number of different time intervals, specifically:
 
 Solicited AEs: within 7 days of first vaccination and also within 7 days after each vaccination Safety laboratory assessments 7 days before and after each vaccination Unsolicited AEs: within 28 days of each vaccination (Days 28, 56, 236) All unsolicited AEs, MAAEs, NOCDs, SAEs, AEs leading to discontinuation/withdrawal up to by time period after the first vaccination Additional supportive analyses are defined in the SAP

Table 7-4 Summary of Statistical Methods and Supportive Analyses

Estimand Label	Estimand Description	Main Estimation			Supportive Analysis
		Analysis Set	Imputation/ Data/ Censoring Rules	Analysis Model/Method	

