9.1. Adverse Events

Adverse Event (AE) collection will begin after the signing of informed consent; however, AEs that occur prior to the administration of first dose of study vaccine (i.e., non-treatment-emergent AEs) will be listed in the clinical study report. MedDRA version 23.0 or higher will be used for coding to System Organ Class (SOC) and Preferred Term.

Any case of confirmed COVID-19 or asymptomatic SARS-CoV-2 infection will be regarded as a Clinical Event of Special Interest (CESI) and entered on the CRF as an Adverse Event. Because CESI events are typically associated with the disease under study, they will not be reported as suspected unexpected serious adverse reaction (SUSAR) but on the CESI eCRF page.

Summaries of number of participants (%) with solicited AEs (by toxicity grade), safety laboratory assessments (by toxicity grade), unsolicited AEs (by severity and relatedness to study vaccine), MAAEs, NOCDs, and AEs leading to discontinuation/withdrawal will be presented and

also with a focus on those related to vaccine administration. All summaries will be evaluated by study treatment group as well as vaccine administration (first dose, second dose, booster dose).

Incomplete AE onset and end dates will be imputed according to the rules specified in [Appendix 2](#).

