Table 13-4: Primary Safety Estimands With Rationale and Strategies to Address Intercurrent Events

Estimand Label	Estimand 1 (Safety)
Estimand Description	Count and percentage of vaccinated healthy adults who would develop MAAEs, NOCDs, SAEs, AEs leading to discontinuation/withdrawal, solicited AEs, and unsolicited AEs: These will be evaluated after each dose of study vaccine by priming vaccine study group and by booster vaccine received (ARCT 021, ARCT 154, ARCT 165, or placebo). A treatment policy strategy is used for assessing safety irrespective of an early infection within 7 days after the first vaccination or an infection during the study or missed subsequent vaccination. Infections and death are included in the endpoint (composite strategy).
Target Population	Participants receiving at least 1 dose of study vaccine (as defined by eligibility criteria).
Endpoint	Occurrence of MAAEs, NOCDs, AEs leading to discontinuation/withdrawal, SAEs, solicited, or unsolicited AEs: 
 Solicited AEs within 7 days of each vaccination (by Toxicity Grade, Appendix 5): Day 7, Day 35, Day 215 Unsolicited AEs within 28 days of each vaccination (by mild/moderate/severe severity): Day 28, Day 56, Day 236 MAAEs, NOCDs, SAEs, AEs leading to discontinuation/withdrawal from vaccination 1 to prior to vaccination 2, vaccination 2 to prior to booster, overall prior to booster vaccination, and post-booster vaccination.
Treatment Conditions	Placebo or 5.0 µg or 7.5 µg ARCT-021 administered on Day 0, Day 28; Placebo, ARCT-021, ARCT-154, or ARCT-165 administered on Day 208.
Population-Level Summary Intercurrent Event Strategy	Percentage of vaccinated participants (who would develop each type of AE).
IcEv1 (Death)	Composite strategy
IcEv2 (Missed second)	Treatment policy strategy
IcEv3 (Immune-modifying)	Treatment policy strategy
IcEv4 (Early infection)	Treatment policy strategy (based on study phase)
IcEv5 (Study infection)	Composite strategy
Rationale for Strategies	Deaths and symptomatic infections during study would contribute as part of the endpoint (i.e., included as MAAEs, SAEs, NOCDs, AEs leading to discontinuation/withdrawal, solicited AEs or unsolicited AEs) as per normal practice. A treatment policy strategy is used for assessing safety irrespective of early infection and missed additional (second, booster) study vaccinations.

Table 13-5 Primary Immunogenicity Estimands With Rationale and Strategies to Address Intercurrent Events

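### The protocol says COVID-19 cases are analysed apart from safety data, yet Estimand 1 and the SAP count them in the overall AE, MAAE and SAE rows, and no planned overall row leaves them out

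*Protocol*

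**What the plan says.** The primary safety objective is comparative: "To assess the safety and reactogenicity of ARCT-021 compared to placebo for priming vaccination" (Protocol 2.1). The documents then give two rules for infections.

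- **Kept apart.** Protocol 6.4.1.1.7 says of CESIs: "These events are analyzed separately from safety data". The exception is signs or symptoms that the investigator thinks more likely due to the vaccine, which are reported as AEs.
- **Counted.** Protocol Table 7-2 assigns study infection a composite strategy for Estimand 1, with the rationale "Deaths and symptomatic infections during study would contribute as part of the endpoint". Table 7-4 repeats this as the data rule for main estimation, for infections that meet the AE and time-window criteria. SAP Table 13-4 carries the same rationale.
- **Recorded as AEs.** SAP 9.1 has any confirmed COVID-19 or asymptomatic infection "entered on the CRF as an Adverse Event". That is wider than the estimand's rationale, which speaks of symptomatic infections only.

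The MAAE definition (Protocol 6.4.1.1.4) names COVID-19 among the unscheduled visits that make an event an MAAE. Protocol 6.1 calls for such a visit when COVID-19 symptoms are confirmed, outside the first 7 days. None of the overall summaries in SAP 9.1.2.1 or 9.1.2.2 excludes infections. SAP section 1 lets the SAP prevail where methods differ, but section 11 does not list this difference.

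**The concern.** An all-cause row that contains the disease the vaccine is meant to prevent mixes two effects: events the vaccine causes and events it averts. If there is any efficacy, placebo carries extra AEs and MAAEs, and the difference from placebo understates a vaccine-caused excess. The MAAE row is the most exposed, because the protocol's own surveillance turns most symptomatic cases into medically attended events. A reader who relies on Protocol 6.4.1.1.7 would take the overall rows to be free of COVID-19, and they are not.

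**Working it through.** 1. **The plan's own safety figure.** Table 7-3 gives the chance of seeing at least one event as 1 − (1 − R)^N. For R = 1% and N = 75 this is 1 − 0.99^75 = 0.529, as stated. It concerns one group and says nothing about a difference from placebo.

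2. **Inputs.** Let b be the background rate of the event class, a the placebo attack rate, VE the efficacy and h the vaccine-caused risk. The documents give none of them; all values below are assumptions. Group size is 75 per Study Group per Age Cohort, so 150 per Study Group.

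3. **Model** (independent risks, each participant counted once):
   - placebo rate = 1 − (1 − b)(1 − a)
   - vaccine rate = 1 − (1 − b)(1 − a(1 − VE))(1 − h)
   - with h = 0, vaccine minus placebo = −(1 − b) × a × VE

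4. **Shift over the priming period:**
   - b = 0: 2% × 0.5 = 1.0 point; 6% × 0.7 = 4.2 points
   - b = 30%: 0.7 × 1.0 = 0.7 point; 0.7 × 4.2 = 2.9 points
   - overall range 0.7 to 4.2 points

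5. **Example with a real harm** (b = 10%, h = 5%, a = 6%, VE = 70%). Without infections the excess is 0.9 × 5% = 4.5 points. With them, placebo is 1 − 0.9 × 0.94 = 15.4% and vaccine is 1 − 0.9 × 0.982 × 0.95 = 16.0%, so the excess shows as 0.6 point.

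6. **28-day AEs.** At constant infection risk, the two 28-day windows cover 56 of the 208 priming days. Before overlap the shift is 1.0 × 56/208 = 0.3 to 4.2 × 56/208 = 1.1 points for both windows together, and half that for one dose.

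7. **Other rows.** SAEs are affected only by serious cases. An NOCD is a new chronic diagnosis, which acute COVID-19 would not ordinarily be. Seven-day solicited AEs leave little time for infection.

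8. **Can the planned tables undo it?** Term-level tables give the number with any event and the number with COVID-19, but not the overlap. The number with any other event lies between (any − COVID-19) and any. With 150 × 2% = 3 to 150 × 6% = 9 placebo cases, that interval is 2 to 6 points wide, so the tables do not settle it.

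**The case against.** The strongest reply is that this is a declared estimand. Counting infections is stated in Protocol Tables 7-2 and 7-4 and in the SAP, and an all-cause rate answers a legitimate question. That stands, and the composite rows should stay. It does not explain why 6.4.1.1.7 says otherwise or why section 11 is silent.

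The second reply is mitigation. Protocol 7.6.3.1 and SAP 9.1.2.1 plan rows for related events, which a COVID-19 case judged unrelated does not enter. SAP 9.4 tabulates COVID-19 and asymptomatic infection by period, and listings would let someone with individual data rebuild the rows. This is real but partial: related rows rest on investigator judgement, and no planned overall output excludes infections.

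Third, the size is assumed and modest. At 150 per group and an assumed 10% event rate, the 95% half-width of a difference is 1.96 × √(2 × 0.1 × 0.9/150) = 6.8 points, larger than the whole range above. Protocol 7.2 plans no hypothesis test, so interpretation is at stake, not type I error.

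Some stronger readings are tempting but unsupported:

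- *That SAEs and NOCDs through Early Termination are hit hardest, with the offset growing over follow-up.* Participants at high risk of severe COVID-19 are excluded (Protocol 4.1.2). Placebo participants may leave and re-enrol from Day 98 under a new ID (5.1) and are summarised separately (7.6.7). Off-study COVID-19 vaccine is allowed (4.2.3). The last two limit growth, and shorter placebo follow-up works against the supposed direction.
- *That Estimand 1 contradicts itself* by applying treatment policy to an early infection "or an infection during the study or missed subsequent vaccination" and composite in the next sentence. Keeping data after an infection and counting the infection are compatible.
- *That Protocol 6.4.1.3.3, "These events will be recorded on the CESI eCRF page", forbids AE entry.* It is an exception to SUSAR reporting, and SAP 9.1 uses both pages.

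**Conclusion.** The conflict between Protocol 6.4.1.1.7 and Estimand 1 with SAP 9.1 is in the current text and unrecorded. The overall unsolicited-AE and MAAE rows will contain infections. Whether this hides anything depends on efficacy, which the documents leave open: Protocol 1.7 says the vaccines may or may not protect. With zero efficacy, nothing is offset apart from slight dilution; under the ranges assumed above, the priming-period shift is large enough to matter when reading an MAAE difference, but within sampling error for one pair of groups. This is a correction to labelling and a missing companion table. It does not show that the safety analysis is invalid or that harm has been concealed.

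**What to change.** State one rule for CESIs in Protocol 6.4.1.1.7, Estimand 1 and SAP 9.1, including whether asymptomatic infections count, and record the resolution in SAP section 11.

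In SAP 9.1.2.1 and 9.1.2.2, add overall unsolicited-AE, MAAE and SAE rows that exclude events meeting the protocol's CESI case definition (RT-PCR or anti-nucleocapsid confirmed). Do not filter on all three COVID-19 preferred terms in SAP Table 13-3. Unconfirmed Suspected COVID-19 events, and symptoms judged more likely vaccine-related, should stay in, because fever, chills, fatigue, myalgia and headache are both solicited reactions and COVID-19 triggers.

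Present the new rows beside the all-cause composite rows and the separate COVID-19 and VAERD assessment, and interpret them together. The excluded version should not be the sole basis for judging harm, since enhanced disease would show up among the infections. The cost is one filtered repeat of the overall summary tables and a few lines of text.
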